Participant Recruitment Mailings**

Providers at the health systems can also refer

potential eligible patients and provide provider referral via fax. Provider referral will be reviewed by a research program manager to determine the eligibility of the patient and to identify if the referred patient is found in the EMR database. We will follow step 3 to reach out to the patient.

2. **Step 2 - Mailed letter of invitation:** The JHU Study Recruitment Center staff mail to potentially eligible patients a packet that includes a letter of invitation describing the opportunity for them to participate in a study for which they may be eligible, a study brochure, a copy of the oral consent, and a pre-posted “opt-out” postcard. If the potential participant pool is large enough, these packets are mailed in batches, beginning with the highest risk patients. The number of packets in a batch varies depending on the number of potentially eligible patients, response rates from previous mailings, etc. Though we are targeting the highest risk patients when possible, we are also sampling patients based on race, ethnicity, and geographic location in order to have fairly balanced groups for analysis.

We are recruiting more than 63 patients at some practices. This is necessary due to the fact that some practices are smaller and therefore have fewer eligible patients from which to select. It is our goal to maintain an average of 63 patients per practice in each health system. Our strategy for recruitment at any practice is to begin recruitment with the racial or ethnic group that has the least representation at that practice, whatever that maybe (i.e., at some practices it may be the white population), in order to maximize possible recruitment in that specific group at that practice.

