1. **Step 3 - Telephone Screening and Oral Consent:** After a waiting period of 10 days, patients who have not contacted the study recruitment center to opt out of the study are followed up by telephone. During the phone call, potentially eligible persons are asked if they are interested in participating in the study. We screen persons (both those contacted by us and those who reach out to us in response to the mailing) for eligibility using a set of prepared questions. Eligible patients who remain interested in the study are read the oral consent form. If the patient agrees to participate, the telephone baseline interview is completed. In cases where patient is unable to complete telephone baseline interview due to limited phone minutes, paper version of the baseline interview will be mailed to the patient with returned envelope. When the baseline data collection has been completed, patients are informed of the assignment group of their practice. If the recruitment goal has not been reached within a reasonable amount of time, we mail another batch of letters and repeat this process until the recruitment goal of an average of 63 participants per practice is met, or recruitment closes at the practice.
2. **A participant is considered enrolled in the study once they have completed the baseline survey.** In order for a participant to successfully complete the baseline survey they must complete the PAM, PHQ, PROMIS Global scale, adverse events questions, and demographics questions. The eligibility BP measurement will be the participant's baseline BP measurement in both arms. Consented participants in both arms will continue to attend their typical schedule of primary care appointments. We do not require a specific frequency of primary care visits during the study period.
3. **Step 4 – First Intervention Visit for Patients in CC/Stepped Care Practices Only:** The First Intervention Visit is conducted by the Care Manager (CM) at the participant's primary care practice. The participant is invited to meet both the CM and CHW. BP, height and weight measurements will be taken by typical personnel and in a manner that follows the practice site's normal procedures. The participant receives and is trained on the use of the home blood pressure monitor.

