4. **Timeline for recruitment and consent:** Recruitment and enrollment of patients begins at least two months after the introduction of the OMRON machines in each practice, which is one month before we introduce the rest of the interventions in both arms. We are estimating that it will take seven months to fully enroll an average of 63 participants at each practice.
5. **Loss to follow up:** We are using a very pragmatic approach to follow-up in the study. If a patient requests to withdraw, no further survey data will be collected for that participant but EMR data will continue to be collected. A patient will be considered lost to follow up if he or she does not have a BP measurement recorded in the EMR within 24 months of enrollment.

To attempt to minimize loss to follow up:

- i. The study will send out a 6- and 18-month survey reminder letter to all study participants two weeks prior to the month in which their follow-up survey call is due.
- ii. The study will send out a 12- and 24-month survey reminder letter to all study participants approximately six weeks prior to the month in which their follow-up survey call is due.
- iii. The study call center will call participants a minimum of six times in the 6 months after the follow up date for the 12 month survey and 6 months after the follow up date for the 24 month survey. The study may also send up to two reminder letters for 12- and 24-month follow-up survey calls. The call center will also reach out to contacts provided by participants to attempt to reach the participant.
- iv. In cases where a patient cannot complete follow-up interviews due to limited phone minutes, we will mail a paper version of follow-up interviews with a return envelope.
- v. In addition, at intensive intervention sites, the CC/Stepped care team will attempt to engage the participants. The team will follow the missed intervention appointment protocol shown in Figure 5.

Figure 5: Missed Intervention Appointment Protocol

F. Participant compensation: Each patient participant will be compensated as follows:

1. Patients in the **CC/Stepped Care arm** receive:

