| Technical Skills | 
 - Physical exam and ROS for systems relevant to CVD and Type II Diabetes - BP measurement according to JNC-8 guidelines - Use of digital equipment - Use of computers |

F. Protocol for Difficult to Engage Patients. CMs should implement the following steps when attempting to engage with patients who have missed first intervention visits or become disengaged: 1) make at least 8 phone attempts for missed FIV appointments and 4 phone attempts for follow-up appointments to engage a patient by phone (phone attempts should be done on different days of the week and at different times of the day); 2) send a “trying to reach you” letter; 3) communicate with the PCP that the CM has had difficulty reaching the patient; 4) monitor the EMR for upcoming patient visits at the practice or other practices both within and outside of the health system, making sure appropriate follow-up occurs by trying to meet the patient at one of these appointments; 5) monitor the EMR and/or CRISP for notifications of patient visits to the emergency department or hospital admissions; 6) conduct an outreach phone call if a patient has been hospitalized or has gone to the emergency department; 7) refer the patient to the CHW if the previously stated actions do not result in successfully engaging with the patient.

G. Plan for Discharging Patients from Care Management. The care manager may discharge patients that achieve and maintain all clinical goals for a period of 6 months AND indicate a preparedness to exit the program. Upon 6 months of clinical goal maintenance, the care manager gauges the patient’s preference for on-going participation by asking if the patient prefers to have the care manager continue to call and check in regularly or if the patient would prefer to reach out to the care manager if they feel they need more support in goal maintenance. The care manager emphasizes that regardless of the patient’s choice, the care manager and study team will remain available to the patient and the study team will continue to call the patient every 6 months to complete study questions. This pragmatic approach for discharging patients factors in the typical resource constraints of care

management programs while emphasizing patient preferences in the patient's care plan. Patient withdrawal criteria is described in *Section 5. Recruitment of Participants, Item C. Withdrawal criteria.*

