For the CC/Stepped Care arm, exploratory analysis will be conducted to determine which parts of the intervention, e.g., number of CM and CHW contacts, were more successful in improving BP control and reducing systolic BP, or if there was an overall “dose” effect.

Power calculation

We aim to recruit a total of $n=1,890$ unique patients. We planned for 20% random attrition which would yield an analytic sample of 1,500 (effective size of 50 patients per practice).^{104,105} A review of cluster-randomized trials in primary care found a median intracluster correlation coefficient (ICC) of 0.04, with an interquartile range of -0.02 to 0.21.¹⁶⁴ Assuming a 5% ICC, 15 clusters of 50 patients per intervention arm and a two-sided alpha of 0.05, we will have 80% power to detect a difference in proportion of patients with BP controlled of 11-13% (depending on whether the proportion controlled in the SCP arm is 50%-70%). With the same assumptions and sample size, using a two-sample t-test, we will be able to detect an effect size of 0.278. Operationalizing this for the primary and important secondary outcomes, we anticipate that for PAM-13, estimating a $SD=10.0$,¹⁶⁵ we would be able to detect a mean difference of 2.78 between the CC/Stepped Care and SCP arms; for systolic BP, estimating a $SD=19.5$ mm Hg,¹⁵³ we could detect a mean difference of 5.42 mm Hg between the CC/Stepped Care and SCP arms.

Design Considerations:

Participants will be considered to be enrolled at the time they are given their randomization assignment, which will occur at the end of the baseline interview. Data from all enrolled participants will be analyzed as intent-to-treat.

Missing Data

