For the Patient Survey (telephone interview) data: To limit missing data at baseline, we are not considering the patient to be enrolled in the study until they complete the baseline survey. We make the participant fully aware of the time involved to complete the survey prior to beginning. We also give the participant the option to complete the survey in more than one telephone call. Our interviewers are trained to encourage the participant to complete the entire survey. Though the participant may choose not to answer some of the questions, we are requiring that they answer at least 10 items of the PAM-13 since this is a primary outcome. Participant data entered into REDCap will be reviewed weekly by the data manager for completeness. If data were inadvertently missing (the participant did not refuse to answer), the interviewer will be asked to re-contact the participant to obtain these data. If there are patterns of missing data across interviewers, we will work to identify why this is occurring and modify training, as necessary, to correct the issue. We are using the scheduling system within REDCap to track when participants are due for follow-up telephone surveys. Additionally, if patients are still being seen at the participating health system, we will have access to updated telephone numbers and addresses. We have tried to minimize study participant burden and follow-up interviews should take less time to complete than the baseline. We will seek to replace dropout patients with others from the same clinic when these occur early in the intervention period. A dropout is defined as any participant who, after completing the baseline survey and receiving their randomization assignment, states that s/he wants to withdraw from the study and receive no further contact from the study team. If this occurs within two (2) months of the date of randomization, we will attempt to recruit an additional patient from the same practice.

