4. *Randomized trial:* The human subjects in this phase of the proposed research are 1,890 patients with hypertension (HTN) and associated comorbidities who receive their primary healthcare at partnering health systems, as well as the clinicians and staff of each practice and leadership of the systems to which the practices belong. The research will include an average of 63 patients at each of the 30 participating practices within these health systems. As our study design is a cluster randomization of practice sites, not participants, patients will be assigned to the study condition, SCP or CC/Stepped Care intervention arm, of the practice they attend for healthcare. Patients are surveyed prior to learning the random assignment of their practice and are given information on each condition and asked if they are willing to participate, given that they may end up in either condition. Clinicians and staff will be asked their opinions about their workplace and their satisfaction with the program. Leaders will be asked about the capacity and priorities of their systems.

b. **Adequacy of Protection Against Risks and Potential Benefits**

- i. **Education in protection of human research participants:** Education in the protection of human research participants and good clinical practice has been met by certified completion of the Johns Hopkins University School of Medicine or School of Public Health Web-based Research Compliance course, “Human Subjects Research Training” by all relevant Key Personnel. The course consists of the University of Minnesota Web modules on Informed Consent, the Consent Process, and After Informed Consent, a Johns Hopkins University School of Medicine module on local IRB requirements, and achievement of a passing score on the Johns Hopkins Knowledge Assessment module. Training in the Health Insurance Portability and Accountability Act (HIPAA) has also been met by certified completion of the Johns Hopkins University School of Medicine’s Web-based HIPAA training course.
- ii. **Recruitment and Informed Consent:**
 1. *Recruitment for Kick-Off/Town Hall Meetings:* Identified stakeholders in the proposed research are invited to attend town hall meetings by letter/email from the Principal Investigators (PIs). Letters are sent at least two months prior to meetings to allow adequate planning time for stakeholders.

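### Recruiting an extra patient when someone withdraws within two months of learning their arm lets enrolment depend on arm; the likely effect on BP control is small, and the rule is not needed

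*Combined protocol and SAP*

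**What the plan says.** The rule is in Section 8, Missing Data. A dropout is a participant who, "after completing the baseline survey and receiving their randomization assignment, states that s/he wants to withdraw from the study" and wants no further contact. The plan continues: "If this occurs within two (2) months of the date of randomization, we will attempt to recruit an additional patient from the same practice". It applies to both arms.

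The surrounding text sets the context:

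- **Disclosure.** Section 5E, Step 3: "When the baseline data collection has been completed, patients are informed of the assignment group of their practice". The human-subjects section, on the randomized trial, agrees: "Patients are surveyed prior to learning the random assignment of their practice".
- **Contact in CC/Stepped Care.** Enrolled patients are scheduled for a First Intervention Visit, within 14 days where possible (Risks to Human Subjects, Patient Recruitment for Trial). If it is missed, care managers are to "make at least 8 phone attempts for missed FIV appointments" (Section 6C, Collaborative Care Intervention, item F).
- **Contact in SCP.** There is no such visit. The first scheduled contact is the 6-month survey and its letter: "The study will send out a 6- and 18-month survey reminder letter to all study participants" (Section 5E.5).
- **Order of recruitment.** Section 5D, Step 2: if the pool is large enough, "these packets are mailed in batches, beginning with the highest risk patients". Recruitment also starts with the racial or ethnic group least represented at the practice.
- **Analysis set and data after withdrawal.** Section 8, Design Considerations: "Data from all enrolled participants will be analyzed as intent-to-treat". Under Section 5E.5, a patient's request to withdraw stops surveys, while EMR collection continues.

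The plan does not say whether the added patients count toward 1,890, whether they are flagged or reported by arm, or whether any sensitivity analysis leaves them out.

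**The concern.** Whether a new patient is enrolled depends on how an earlier patient reacted after learning the arm. In the two months that count, CC/Stepped Care patients are called, scheduled and followed up, while SCP patients have no scheduled study contact. Scheduled occasions to ask for no further contact are therefore concentrated in one arm, and the number of added patients could differ between arms.

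The added patients need not resemble those recruited first. In practices that mailed by risk, they would tend to be lower-ranked. If that goes with better BP control at 12 months, and if more are added in CC/Stepped Care, that arm gains slightly for a reason unrelated to treatment.

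For PAM-13 the issue is different. An early dropout has no 12-month score, whereas the added patient can supply one. The count of completers can then look healthy in an arm that lost patients because of its own contact schedule, although the power calculation treats attrition as random.

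**Working it through.** **1. Reproduce the plan's detectable differences (Section 8, Power calculation).** Inputs: 15 practices of 50 patients per arm, ICC 0.05, two-sided alpha 0.05, 80% power.

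- Design effect = 1 + (50 - 1) x 0.05 = 3.45.
- Effective n per arm = 750 / 3.45 = 217.4.
- Detectable effect, t-test on 28 df (30 practices less 2) = 0.2784, against the stated 0.278.
- Detectable difference in BP control (normal approximation) = 13.3, 12.7 and 11.5 points at SCP control of 50%, 60% and 70%, against the stated 11-13.

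The stated figures reproduce.

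**2. Is replacement needed for power?** 1,890 x 0.8 = 1,512, against the 1,500 used. Suppose a further 5% were lost in both arms, leaving 47.5 per practice. The design effect is 1 + 46.5 x 0.05 = 3.325, and effective n = 712.5 / 3.325 = 214.3. The detectable effect becomes 0.2784 x sqrt(217.4 / 214.3) = 0.280. The loss is negligible.

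**3. Possible shift in BP control.** Let f be the share of an arm replaced early, and g the gap in 12-month BP control between added patients and those they join. The documents give neither, so both are assumed. With dropouts kept in the analysis, added patients make up f / (1 + f) of the arm, and the between-arm shift is

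g x [f_CC / (1 + f_CC) - f_SCP / (1 + f_SCP)].

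With 1,890 / 2 = 945 patients per arm and no replacement in SCP:

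| f in CC/Stepped Care | Patients added | Shift, g = 10 points | Shift, g = 20 points |
|---|---|---|---|
| 2% | 19 | 0.20 | 0.39 |
| 5% | 47 | 0.48 | 0.95 |
| 10% | 94 | 0.91 | 1.82 |

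For example, 0.10 / 1.10 x 20 = 1.82. If SCP also replaced 2%, that largest value falls to 1.43. With equal shares and gaps in both arms it is zero.

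**4. Effect on the false-positive rate.** With no true effect and 60% control in both arms, the standard error is sqrt(2 x 0.6 x 0.4 / 217.4) = 4.7 points. On 28 df, a shift of about 0.5 points raises two-sided rejection from 5.0% to 5.1%, 1 point to 5.5%, and 2 points to 7.0%.

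**5. PAM-13 completers.** Take f = 5% in CC/Stepped Care and ignore other attrition. Without replacement, 945 - 47 = 898 patients can give a 12-month score. With replacement, 898 + 47 = 945 can, which equals the target. The loss is hidden unless dropouts and added patients are counted separately.

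**The case against.** The strongest reply is that an arm difference is conjecture. The rule covers both arms, and patients in both learn their assignment at the end of baseline and can withdraw then. Re-contact for missing baseline items can occur in either arm. A missed First Intervention Visit is not a dropout, because an explicit request for no further contact is required, and the eight calls lead on to a CHW referral rather than to withdrawal. Risk-ordered mailing is conditional on pool size. Nothing in the documents shows that rank predicts 12-month control, and all patients qualify with systolic BP of at least 140 mm Hg. All of this stands, and it is why the shift is put as a possibility with assumed inputs. It does not remove the imbalance in scheduled contact, or the lack of any tracking of replacements.

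Four stronger readings are tempting, and the documents do not support them:

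- *That one arm is filled with willing patients.* Added patients consent and complete baseline before learning the arm, as the first recruits did, so they are not selected for accepting intensive contact.
- *That only CC/Stepped Care is topped up.* The rule is common to both arms and no withdrawal rates are given.
- *That replacing dropouts conflicts with intent-to-treat.* The operative sentence adds a patient; nothing removes the dropout. Section 8 keeps everyone enrolled, and EMR blood pressure continues to be collected.
- *That the two-month clock had expired before enrolment*, since health systems learned the allocation in March 2017 and patient recruitment began in August 2017. Design Considerations places the patient's randomization assignment at the end of the baseline interview, and the dropout definition uses the term the same way. In context, the date is the patient's own.

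It is also fair to say that deleting the rule recovers no missing PAM-13 scores. Those remain for the planned missing-at-random and informative-missingness analyses.

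**Conclusion.** The point holds in a limited form. The rule allows enrolment to depend on reactions to the disclosed arm, in a window when scheduled study contact exists in one arm only, and the plan provides no tracking or sensitivity analysis. That more patients are added in CC/Stepped Care, and that they are lower-risk, are inferences; the second applies only where mailing followed risk order.

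For BP control the expected effect is small: about 0.2 to 1.8 points, against 11-13 detectable. That range rests on assumed early replacement of 2-10% in CC/Stepped Care and none in SCP, a 10-20 point gap in control, and dropouts kept in the analysis as the plan requires. For PAM-13 no size can be given; the problem is that arm-related attrition may be masked. This is a cheap improvement and not a threat to the trial's main conclusion.

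**What to change.** Delete the replacement rule from Section 8, Missing Data, and rely on the 20% attrition allowance. The cost is a slightly smaller sample in practices with early withdrawals.

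This version carries a footer date of 10.15.21, and Section 7C already counts about 588 participants still to complete 24-month follow-up, so enrolment has probably ended. If replacements have been enrolled:

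- flag each one;
- report early dropouts and replacements by arm;
- repeat both primary analyses, BP control and PAM-13, without the replacements, keeping early dropouts in the intent-to-treat set as Section 8 already states.

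This costs one flag variable, one table and one extra run of each primary model.
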